## **Ethics and dissemination**

This study is approved by the University of Pennsylvania Institutional Review Board (IRB # 829765) and informed consent will be obtained prior to enrollment. The dataset supporting the results of this study will be available in the Zenodo research data repository. This study is registered with ClinicalTrials.gov at NCT05330676.

## **Status and timeline of the study**

Initial pilot testing, staff education, and laboratory calibration testing began recruitment of the participants began on September 1, 2020. The study is actively enrolling subjects at the time of this publication. Preliminary analysis of microcirculation images, mitochondrial respiration, and VVFDs will be conducted in 2022.

## **SAFETY MANAGEMENT**

### **Clinical Adverse Events**

Clinical adverse events (AEs) will be monitored throughout the study.

### **Adverse Event Reporting**

Since the study procedures are not greater than minimal risk, SAEs are not expected. If any unanticipated problems related to the research involving risks to subjects or others happen during the course of this study (including SAEs) these will be reported to the IRB. AEs that are not serious but that are notable and could involve risks to subjects will be summarized in narrative or other format and submitted to the IRB at the time of continuing review.

### **Safety considerations**

The Principal Investigator will be primarily responsible for the study conduction throughout protocol completion. Research personnel will be required to report any relevant protocol deviations or research related adverse events to the Principal Investigator. Risks associated with sublingual IDF imaging are low and no identifiable adverse events have been previously linked to sublingual IDF imaging.

## STUDY ADMINISTRATION

### Data Collection and Management

Data abstracted from the medical record will be managed and stored using the research-focused electronic data capture system REDCap (Research Electronic Data Capture) under an agreement with the software's development consortium, led by Vanderbilt University. We will use the REDCap server located at HUP.

Data will be managed and stored using the research-focused electronic data capture system REDCap, under an agreement with the software's development consortium, led by Vanderbilt University. REDCap supports two secure, web-based applications designed exclusively to support data capture for research studies.

REDCap as implemented at HUP includes daily destructive database backup files that are stored on the database server and are deleted only after successful backup of the entire database to file. Data and backups are stored in the HUP Research Information Systems Storage Area Network (SAN). Access to the SAN directories where data are stored will be limited to Research Information Systems personnel, with authentication performed using HUP's enterprise Active Directory service.

Each study patient will be given a study identification number (study ID). Only the study ID will be recorded on the CRF. A master list linking the study ID to identifying information will be kept separate from the CRF and stored as a locked Excel file on the hospital's secure servers. Dates (e.g., date of birth, date of hospitalization, date of study enrollment) will be recorded in REDCap in order to determine age, length of stay, etc. However, **only coded data will be exported from REDCap to be used for analysis of study results.** We will use the automated feature within REDCap to shift all dates by a value between 0 and 364 days. Date shifting is important for de-identification because dates are identifiers that can be used for identifying an individual and thus possibly exposing confidential personal information. Date shifting will prevent any dates from being used as identifiers while preserving the interval between dates so that age can be calculated. Date shifting will be used to de-identify data prior to sharing with colleagues at Penn. Access to PHI (i.e the master list and dates in REDCap) will be limited to the PHI and key study personnel at HUP. Those not involved in data entry will not have access to view PHI (i.e., dates) within REDCap (using REDCap's security features to limit data access) and will be limited to viewing coded data and shifted dates only. If paper versions of the CRF are needed (e.g., temporary loss of access to REDCap), these will be kept in a locked cabinet in the PI's office and will be coded using the study ID. Only study personnel authorized by the IRB will have access to study-related data and files.

The password-protected master list linking patient identifiers to the study ID will be retained indefinitely.

### Data sources

This study will in no way alter or interfere with the clinical care of any shock or control subject as determined by the medical care team. All clinical data will be abstracted from the paper or electronic (EPIC and Sunrise) medical record. To assist in this effort, we will perform manual review of the medical record for each study patient. At HUP, each data collector and the Data Coordinator have completed extensive initial training and monitor data quality quarterly, including inter-rater reliability.

### Confidentiality

All data and records generated during this study will be kept confidential in accordance with Institutional policies and HIPAA on subject privacy and that the Investigator and other site personnel will not use such data and records for any purpose other than conducting the study. Safeguards to maintain subject confidentiality are described under Data Collection and Management.

Confidentiality of the data will be ensured by keeping a master list containing patient identifiers and study ID separate from data forms (paper and electronic). The master list will be kept in a locked file on the password-protected computer of the PI, with a paper copy stored in a locked file cabinet in the PI's office. All study-

related files will be password-protected. Patient identifiers, including the master list, will be destroyed within three years after publication.

For data security, a copy of all password-protected files will be maintained on the Investigator's office computer (which itself is password-protected), with the original in one of the Hospital's secure servers.

No identifiable data will be used for future study without first obtaining IRB approval. The investigator will obtain a data use agreement between provider (the PI) and any recipient researchers (including others at HUP) before sharing a limited dataset (dates and zip codes). Samples processed in the Metabolomics lab and the will be coded with a study ID only and PHI will not be shared.

## **Regulatory and Ethical Considerations**

### **Data and Safety Monitoring Plan**

The systems for storing and backing up data were described above. The principal investigator will be responsible for monitoring data collection and the safety of all study measurements. Given the minimal risks and observational nature of the study, we do not require an independent medical monitor of safety.

### **Risk Assessment**

The risks for patients participating in this study are not greater than minimal risk and include those related to 1) blood collection for study measurements and 2) breach of confidentiality.

Since we will limit the volume of blood collection to less than 3 mL/kg or 50 mL and no more than two blood collections in one week, this falls under the provision of "not greater than minimal risk." For any patient whose clinical condition might be adversely affected by removal of the stated blood volume for this study (e.g., patients with significant anemia or compromised cardiac output), we will discuss further limiting the volume of blood withdrawn for research purposes with the patient's attending physician. Any patient concurrently enrolled in another study for who enrollment in this study would mean the combined blood volume collection would exceed IRB regulations will be excluded from participation in this study. Finally, since patients with shock typically undergo multiple blood draws per day and often have central and/or arterial vascular access devices, whenever possible blood sampling for study purposes will be timed with other clinically indicated blood draws or catheter access in order to limit pain from venopuncture, arterial puncture, and access to indwelling vascular catheters. Only caregivers with expertise and training in venopuncture, arterial puncture, or access of indwelling catheters will be permitted to collect blood specimens for this study.

In the rare cases where phlebotomy is performed for study purposes only, attempts will be made to mitigate patient discomfort by using topical anesthetics, such as EMLA. Also, risks will be minimized by limiting the number of attempts to obtain blood to 2 per patient per day and only individuals skilled at performing phlebotomy will be permitted to attempt.

To minimize a potential breach of patient confidentiality, CRFs will be coded with a study ID, all data will be password-protected, and the safeguards to ensure confidentiality as described.

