### **Methods and analysis**

This will be a prospective, observational study that includes patients undergoing elective cardiovascular surgery with cardiopulmonary bypass (CPB). Microcirculation will be quantified with sublingual incident dark field videomicroscopy. Mitochondrial respiration will be measured by performing a substrate-uncoupler-inhibitor titration protocol with high resolution respirometry on peripheral blood mononuclear cells at baseline and serial timepoints during resuscitation and at recovery as a possible liquid biomarker. Plasma samples will be preserved for future analysis to examine endothelial injury and other mechanisms of microcirculatory dysfunction. Thirty-day ventilator and vasopressor-free days (VVFDs) will be measured as a primary outcome, along with sequential organ failure assessment scores, and other clinical parameters to determine if changes in microcirculation and mitochondrial respiration are more strongly associated with clinical outcomes compared to traditional resuscitation targets.

This will be the first prospective study to examine both microcirculatory and mitochondrial function in human patients with circulatory shock undergoing cardiac bypass and address a key mechanistic knowledge gap in the cardiovascular literature. The results of this study will direct future research efforts and therapeutic development for patients with shock.

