## Materials and methods

### Study objective

The primary objective of the MicroRESUS study is to evaluate the microcirculatory and mitochondrial function in patients following elective cardiovascular surgery with cardiopulmonary bypass, to determine if these parameters outperform traditional biomarkers and global hemodynamic measurements to predict clinical outcomes.

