## **Timeline and techniques for data collection**

Data for each subject will be collected at time points outlined in **Error! Reference source not found.** Prior to surgery, baseline biologic samples, microcirculation imaging, and clinical data will be obtained. Repeated measurements will be obtained in the ICU and surgical floor. Long-term clinical outcomes will be recorded at 30-days or upon discharge.

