### Incident Dark Field Microscopy

Sublingual microcirculation imaging will be performed using handheld incident dark field (IDF) videomicroscopy (CytoCam, Braedius Medical BV, the Netherlands) at four time points during the enrollment period. Imaging will be performed by the Principal Investigator or trained research personnel. Video sequences are obtained by placing the CytoCam device in the sublingual space and maneuvered so that pressure and motion do not result in image artifact (**Error! Reference source not found.**). A series of successive video clips (3-5 clips of at least 120 frames or 6 seconds in length) should be captured in distinct areas of the sublingual space to account for vessel heterogeneity. Focus and lighting during video capture may be adjusted to optimize image acquisition. Baseline ( $T_{0h}$ ) imaging will be obtained in the preoperative area prior to surgery on the day of the scheduled operation. Repeated measurements will be obtained upon arrival to the ICU (0-2 hours after surgery,  $T_{2h}$ ), during ongoing resuscitation (2-4 hours post-op,  $T_{4h}$ ), and on post-operative day one after recovery ( $T_{24h}$ ).

**Fig 2. A. Experimental setup with patient in supine position during IDF measurement. B. Anatomical sublingual triangle where measurements are obtained.**

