#### Biological samples

Blood gas samples will be drawn into a commercial, pre-heparinized 1 mL blood sampler then immediately analyzed by an ABL90 FLEX automatic blood gas analyzer (Radiometer America Inc., Brea, California, USA). Arterial blood gas samples will be obtained by clinical staff every 1-2 hours for the first 6 hours after ICU admission based on current clinical practice. Central venous blood gas measurements will also be obtained by the study team at the time of microcirculation measurement. Hemoglobin, hematocrit, pH, PaO2, PaCO2, and glucose are also reported on each blood gas analysis. After 6 hours, blood gas analysis will be performed as needed by the clinical team. For biomarker and mitochondrial function analysis, enrolled patients will undergo phlebotomy with volumes of 15 mL drawn into K2EDTA tubes. Blood samples will then be centrifuged at room temperature using Ficoll-PaqueTM PLUS (GE) and Leucosep tubes (Greiner Bio-one). Plasma specimens will be stored at -80°C for later evaluation of the mechanisms of microcirculatory dysfunction. Peripheral blood mononuclear cells (PBMCs) will undergo further analysis and processing as detailed below.

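### The minimal-risk statement allows two study blood collections in a week, but the sampling plan needs at least three by postoperative day one

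*Combined protocol and SAP*

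**What the plan says.** Risk Assessment gives two conditions as the reason the study counts as minimal risk. One is a volume limit, expressed as 3 mL/kg or 50 mL. The other is a count: "no more than two blood collections in one week". The same paragraph says that study sampling will be timed with clinical draws or catheter access where possible.

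The sampling plan is spread over several sections:

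- Methods and analysis (Abstract) places PBMC respirometry "at baseline and serial timepoints during resuscitation and at recovery".
- Timeline and techniques for data collection confirms the preoperative sample: "Prior to surgery, baseline biologic samples, microcirculation imaging, and clinical data will be obtained".
- Biological samples gives the source and volume: "enrolled patients will undergo phlebotomy with volumes of 15 mL". It also schedules study gases: "Central venous blood gas measurements will also be obtained by the study team at the time of microcirculation measurement". On the gas syringe it says: "Blood gas samples will be drawn into a commercial, pre-heparinized 1 mL blood sampler".
- Mitochondrial respiration requires the cells to be isolated and analyzed within an hour of sampling.
- Incident Dark Field Microscopy sets four imaging times: before surgery, 0-2 hours and 2-4 hours after it, "and on post-operative day one after recovery".

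**The concern.** The count is offered as a ground for the risk classification, and the rest of the protocol relies on that classification. Data and Safety Monitoring Plan dispenses with an independent safety monitor because risk is minimal, and Adverse Event Reporting expects no serious events for the same reason. If the sampling plan cannot meet the count, the protocol claims a protection that its own design does not provide.

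Staff would then have to exceed a stated limit or drop planned samples. Dropping samples would matter scientifically. Study objective sets out to "evaluate the microcirculatory and mitochondrial function in patients following elective cardiovascular surgery with cardiopulmonary bypass", and Statistical and analysis plans compares mitochondrial respiration and reactive oxygen species over time by repeated-measures ANOVA.

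**Working it through.** **Inputs.** Limit on collections: 2 per week (Risk Assessment). Volume per research draw: 15 mL (Biological samples). Gas sample: 1 mL (Biological samples). Respirometry phases: baseline, resuscitation (worded in the plural) and recovery (Methods and analysis). Processing window: 1 hour (Mitochondrial respiration). Imaging times: 4, of which 3 are after surgery (Incident Dark Field Microscopy).

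**Step 1: can one draw serve two phases?** No. Baseline precedes the operation, resuscitation is in the hours after it, and recovery is on the next day on the imaging schedule. With a 1-hour processing window, each phase needs a fresh sample.

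**Step 2: count of PBMC draws.**

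- Minimum: 1 (baseline) + 1 (resuscitation) + 1 (recovery) = 3.
- Taking the plural as two resuscitation draws: 1 + 2 + 1 = 4.
- Both exceed 2.

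**Step 3: does the count depend on when recovery is sampled?** The postoperative day one timing comes from the imaging schedule, and no sentence ties the PBMC recovery draw to it. If recovery were sampled more than a week later, baseline plus two resuscitation draws would still be 1 + 2 = 3 within the week.

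**Step 4: study gases, counted separately.** The study team takes a central venous gas with each imaging session. The postoperative sessions alone give 3 by day one, and all four sessions give 4. Either number exceeds 2 without any PBMC draw.

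**Step 5: volume.** Volume = draws × 15 mL + gases × 1 mL.

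| PBMC draws | Draws only | With 3 gases | With 4 gases |
|---|---|---|---|
| 2 (the stated limit) | 30 mL | 33 mL | 34 mL |
| 3 | 45 mL | 48 mL | 49 mL |
| 4 | 60 mL | 63 mL | 64 mL |

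Three draws stay under 50 mL in every column. Four draws exceed 50 mL, but that is a breach only if the lesser of the two volume limits governs. If 3 mL/kg governed instead, 64 mL would be within the limit for anyone above 64 / 3 = 21.3 kg.

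**Step 6: draw size if four are intended and 50 mL governs.** Without gases: 50 / 4 = 12.5 mL. With four gases: (50 − 4) / 4 = 11.5 mL. Each draw would have to be below that figure.

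**The case against.** The best defence is that collection is undefined. If it means a separate phlebotomy done only for the study, samples taken from a line during a clinical draw would not count, and Risk Assessment describes study-only phlebotomy as rare. This is arguable, and the 1 mL gas syringe does not refute it, because the size of that syringe does not limit what else is drawn at the same line access. But the limit carries no such exemption. Co-timing is presented as a way to reduce pain, the samples are still described as taken for study purposes, and catheter access is listed among the ways of collecting study specimens. The remark about rare cases introduces topical anaesthetic and does not narrow the limit.

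A second defence is that the timeline figure is not available here, so the exact number of draws cannot be confirmed. That is true, and it is why the count is given as at least three. The text alone exceeds two by more than one route.

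Three stronger readings are tempting, and the documents do not support them:

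- *The volume limit is broken.* Three draws fit under 50 mL. Four exceed it only if the lesser limit applies, and the text does not say so.
- *Mitochondrial timepoints will be lost.* That follows only if the two-collection limit is enforced as written. In that case three phases would become two, and pairwise time contrasts would fall from 3 to 1.
- *The main outcome analysis is compromised.* The comparison of VVFDs by PVD uses imaging. The ROC variables listed in Statistical and analysis plans include no mitochondrial measure.

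**Conclusion.** The inconsistency is real. A limit of two collections per week is cited in support of the risk category, and the planned sampling needs at least three, or four if two resuscitation draws are meant. The study gases exceed two independently.

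This rests on two assumptions: that a study sample taken alongside a clinical draw is still a collection, which is the natural reading of the text, and that at least three of the samples fall within one week, which the schedule indicates. Reading 15 mL as the volume of each draw affects only the volume totals. A reader might go on to infer that the study is not in fact minimal risk. The documents do not show that; they show only that one stated ground for the classification does not match the design. No bias or loss of power in the VVFD comparison follows.

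**What to change.** In Risk Assessment:

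- Replace the two-per-week limit with the actual number of study collections, and say whether study gases and samples shared with clinical draws are counted.
- State the total volume: 45 mL for three 15 mL draws and up to 49 mL with gases, or 60 to 64 mL for four.
- State that the lesser of 3 mL/kg and 50 mL applies.
- If four draws are intended, reduce the volume of each so that the total stays under that cap (below 11.5 mL with four gases, below 12.5 mL without), provided the yield still gives the 4-5 million PBMCs that respirometry uses.

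Keep the planned respirometry timepoints; do not cut them to two to preserve the sentence. Submit the change to the IRB and ask it to confirm the risk category, because the count is a stated ground for that category and correcting the number alone is not enough.

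The cost is one IRB amendment and a slightly less favourable risk statement. If draws are made smaller, there may be less plasma and fewer cells to store. No extra patients or procedures are needed, and the VVFD analysis does not change.

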### **Potential Benefits of Study Participation**

There are no direct benefits to patients as a result of participation in this study.

The indirect benefits of this study are clear. The knowledge gained through participation may lead to improved diagnosis, prognosis, and therapy for adults with life-threatening shock and will advance the state of knowledge about progressive organ dysfunction in postoperative shock. The data gathered from this study will be used to inform subsequent studies in shock.

### **Risk-Benefit Assessment**

Given the minimal risk profile associated with this study, the overall benefits to science, medicine, future generations of postoperative individuals, and society as a whole outweigh the risks.

## **Informed Consent/Accent and HIPAA Authorization**

For patients who meet criteria, the patient or next of kin/power of attorney will be approached for study enrollment. The PI, co-investigators, or trained staff members will engage them in a discussion regarding reasons for the study, the study procedures, and the risks and benefits and answer all questions. Due to the often critical nature of the patients' conditions in the inpatient floor, preoperative clinic, or intensive care unit, this discussion may take place at the patient's bedside or in an alternative location (e.g., family conference room) at the next of kin or power of attorney's option and the study investigator's discretion. Also, since it is common for the next of kin or power of attorney to be away from the bedside, we anticipate the need to seek consent over the phone for many patients. Regardless of the where this discussion takes place (i.e., in person or via telephone), all reasonable safeguards to ensure patient privacy will be taken. Next of kin/power of attorney will be given sufficient (i.e., up to several hours) to make a decision to participate in this study.

Following the above conversation seeking informed consent from each patient or their surrogate decision maker and ensuring that this party understand the study objectives and procedures, we will obtain written permission on the combined consent-HIPAA authorization form for all patients for whom the parent/guardian is physically present. If the next of kin/power of attorney is not physically present, we seek a waiver of documentation of consent and HIPAA Authorization to obtain verbal consent, which will be documented on the standard consent form that will be read to subjects with a verbal consent documentation page. At any point during the study time period, patients will be able to withdrawal themselves from the study, as critically ill patients may regain capacity to make decisions regarding the study.

We will provide a copy of the combined consent-HIPAA authorization document to the party and patient and will write a note in the patient's medical record documenting the informed consent discussion.

If the next of kin/power of attorney consents to participate in the study, the next of kin/power of attorney and patient will be notified that any remaining blood samples may be stored in a coded fashion for possible use in future research. Next of kin/power of attorney and patients will have the opportunity to decline use of remaining blood samples for future research. All stored blood samples will be labeled only with a coded study identification number that will be linked to patient identifiers via a master list kept separate from these samples in the PI's locked electronic and/or paper files.

